Describe your ability to obtain access to the proposed population that will allow recruitment of the necessary number of participants: Between several weeks to days before surgery, patients will report to the Highlands Preoperative assessment Clinic (HPAC) for standard of care preoperative health examination and testing by the anesthesiologist attending in HPAC. This visit occurs routinely for patients having surgery in our health system and does not occur because of this study. The anesthesiology attending physician in HPAC, who has routine access to the patient's medical history, will contact the PI or co-investigator should a patient appear to be a candidate for this study based on their routine review of records.

During the patient's visit they will be given a "Patient Information Sheet," describing the study.

On the day of surgery, patients scheduled for surgery will be seen in the preoperative holding area and enrolled in the study if they choose and are appropriate candidates.

d. Describe the inclusion/exclusion criteria:

Inclusion Criteria:

Patients undergoing total knee arthroplasty under spinal anesthesia.

Patients 18 years of age or older.

Patients classified by the American Society of Anesthesiology (ASA) class I, II, or III.

Exclusion Criteria;

Any patient not classified as an ASA I, II, or III.

Patients with hearing impairment, defined by personal endorsement of hearing impairment or use of hearing aids.

Patients with contraindication to spinal anesthesia.

e. If participants will comprise more than one group or stratification, describe each group (e.g., treatment/intervention, placebo, controls, sham treatment) and provide the number of participants anticipated in each group.

Upon enrollment in the study, participants will be randomized 1:1 to either the investigational group ("Music Therapy" group) or the control group ("No Music" group). Participants will be randomized using a random number generator.

f. I	ndicate which, if any, of the special populations listed below will be involved in the protocol. Include the
	Special Populations Review Form (SPRF) if indicated.
	☐ Pregnant Women: Attach SPRF—Pregnant Women, Fetuses, Neonates/Nonviable Neonates
	☐ Fetuses: Attach SPRF—Pregnant Women, Fetuses, Neonates/Nonviable Neonates
	☐ Neonates/Nonviable Neonates: SPRF—Pregnant Women, Fetuses, Neonates/Nonviable Neonates
	☐ Prisoners: Attach SPRF—Prisoners
	☐ Minors (<18 years old): Attach SPRF—Minors

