 - A. Patients who consent to the study will be randomized 1:1 to either the investigational group ("Music Therapy" group) or the control group ("No Music" group). Participants will be randomized using a random number generator.
 - B. Consent and study enrollment will occur in the preoperative area prior to surgery. After enrollment, all patients will complete a State-Trait Anxiety Assessment (STAI) questionnaire. Patients in the "Music Therapy" group will be asked to choose a genre of music that they would like to listen to during the operation (instrumental, jazz, classical, rock, R&B/hip-hop, pop, country, Christian/gospel, musical theatre). All patients enrolled in the study will continue to receive routine preoperative care.
 - a. After proceeding to the operating room, all patients will receive routine preoperative care during placement of spinal anesthesia. In addition to monitors routinely placed prior to spinal block, a BIS (Bi-Spectral Index) monitor will be placed on the patient's forehead to monitor sedation levels during the procedure. A BIS monitor is a noninvasive series of patches placed on the patient's forehead that, through a propriety equation creates a number (1-100) from processed EEG waves that correlates with depth of sedation or anesthesia. After the spinal anesthetic block is placed, the patients in the "Music Therapy" group will wear headphones that will play their pre-selected music. The "No Music" group will receive intraoperative standard of care with no headphones. Headphones will be worn by the "Music Therapy" patients until the procedure is finished (skin incision is closed).

- C. During the procedure, routine intraoperative sedation consisting of propofol, fentanyl and midazolam will be administered. All patients <70 years old will be given 1 mg midazolam, 50 mcg fentanyl and propofol dosing titrated to a BIS level of 60-70 (or as respiratory rate allows), which correlates to moderate sedation. Those patients of age >/= 70 years will receive 50mcg of fentanyl after the spinal with an additional 50mcg only if needed. Again, propofol dosing should be titrated to reach a BIS of 60-70 (or as respiratory rate allows).
- D. All patients will receive standard postoperative care in the post-anesthesia care unit (PACU).
- E. On postoperative day 1, all patients will again complete a STAI questionnaire. Additionally, they will complete a Satisfaction survey.

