- F. The amount of pain medication you received in the operating room will be recorded.
- G. Failed or unsuccessful spinals will be excluded from the study.
- **b.** What is the probable length of time required for the entire protocol (i.e., recruitment through data analysis to study closure)? **1 year**
 - c. What is the total amount of time each participant will be involved? Each participant will be involved in the study for approximately 24 hours. Each procedure time period is listed below.
 - **d.** If different phases are involved, what is the duration of each phase in which the participants will be involved? If no phases are involved, enter "None." **None**
 - e. List the procedures, the length of time the procedure takes, the total # of times the procedure is performed, and indicate whether each is performed solely for research or would already be performed for treatment or diagnostic purposes (routine care) for the population.
 - -Insert additional table rows as needed.
 - -If procedure is sometimes research and sometimes routine care, include on separate lines with number of times as each.

Procedure	Length of Time Required of Participants	Frequency of Repetition	Research (Res) – OR- Routine Care
Presurgical Evaluation on the day of surgery	30 minutes	once	☐Res ⊠Routine
Obtaining informed consent from patient	20 minutes	Once	⊠Res □Routine
Randomization on day of surgery	5 minutes	Once	⊠Res □Routine
Choosing music genre, completing STAI Questionnaire	Approximately 30 min.	Once	⊠Res □Routine
Postoperative day 1: Completing STAI Questionnaire, Satisfaction Survey	20 minutes	Once	⊠Res □Routine

If Yes, attach a copy.	
g. Will participants incur any costs as a result of their participation? If Yes, describe the reason for and amount of each foreseeable cost	□Yes ⊠No
h. Will participants be compensated? If Yes, complete i-v. i. Type: (e.g., cash, check, gift card, merchandise): ii. Amount or Value: iii. Method (e.g., mail, at visit): iv. Timing of Payments: (e.g., every visit, each month): v. Maximum Amount of Compensation per Participant:	□Yes ⊠No
18. Benefits Describe the potential benefits of the research. Music could be a cost-effective way to low requirements, decrease the stress response to surgery and improve patient experience satisfaction during total knee arthroplasty surgery. With lower sedation requirements, may recover sooner, which could impact their recovery in a favorable manner.	and

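### Patients are randomised before the spinal and failed spinals are then excluded without definition or time point, so randomised patients are dropped and some exclusions can be made with the arm known

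*Combined protocol and SAP*

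**What the plan says.** The order of events comes from items 16.e and 17 of the protocol.

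- **Allocation.** Item 16.e: "Upon enrollment in the study, participants will be randomized 1:1". Item 17, step B, gives the place: "Consent and study enrollment will occur in the preoperative area prior to surgery". The procedure table in item 17.e also lists randomisation ahead of the genre choice and the first STAI.
- **Arm known before theatre.** In step B only the music arm "will be asked to choose a genre of music that they would like to listen to during the operation".
- **Start of treatment.** Once the block has been placed, the music "group will wear headphones that will play their pre-selected music", while the control "group will receive intraoperative standard of care with no headphones". No check that the block works is named before the headphones go on.
- **Exclusion.** Step G: "Failed or unsuccessful spinals will be excluded from the study". It has no criterion, time limit or assessor, and no provision for replacement or follow-up.

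The Statistical Considerations section defines no intention-to-treat or other analysis population.

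**The concern.** A working spinal is in effect the last eligibility condition, but it is tested after allocation. Step G therefore removes patients who have already been randomised.

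Two kinds of failure fall under the rule as written. A block that fails before the headphones go on costs patients, and causes little bias if it is judged without regard to arm. A block judged inadequate later is different, because music may already be playing and the staff making the call can see who has headphones. An inadequate block could plausibly show itself as discomfort or a need for more sedation. Anxiety, sedation requirement and satisfaction are the three primary end points in item 14.b. Exclusion could then depend on something that the treatment is meant to change, and the remaining patients would no longer be a randomised comparison.

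This is separate from item 20.b, which removes patients who cannot tolerate headphones. That can happen only in the music arm, whereas step G applies to both.

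**Working it through.** **Inputs from the plan** (Statistical Power and Sample Size Estimates): total sample 100, hence 50 per arm at 1:1; SD 10; target difference 5 STAI points; alpha 0.05. **Not in the plan, so assumed:** the share of failed spinals, the split by arm, and how much worse excluded patients would score.

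**1. The plan's own power figure.** The plan gives about 85% for 25 per group. With SE = 10 × √(2/n) and two-sided power = Φ(5/SE − 1.96):
- n = 25: SE = 2.83, 5/SE = 1.77, power = 42.4%.
- n = 50: SE = 2.00, 5/SE = 2.50, power = 70.5%.

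The 85% is not reproduced. That is a separate matter and this point does not depend on it. I use 50 per arm below.

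**2. Loss of power from exclusion.** Patients left per arm = 100 × (1 − f)/2, where f is the assumed share excluded.

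| f | Excluded | Left per arm | Power |
|---|---|---|---|
| 0 | 0 | 50 | 70.5% |
| 1% | 1 | 49.5 | 70.1% |
| 2% | 2 | 49 | 69.7% |
| 5% | 5 | 47.5 | 68.3% |
| 10% | 10 | 45 | 66.0% |

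The loss is 70.5 − 68.3 = 2.2 percentage points at 5%, and 4.5 at 10%.

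**3. Possible shift in the STAI difference.** If excluded patients score D points above those who stay, dropping them lowers the arm mean by (excluded/50) × D. With D = 10 (one SD):

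| Excluded, control v music | Fall in control mean | Fall in music mean | Shift in difference |
|---|---|---|---|
| 4 v 1 | 4/50 × 10 = 0.8 | 1/50 × 10 = 0.2 | 0.6, against music |
| 3 v 1 | 0.6 | 0.2 | 0.4, against music |
| 1 v 4 | 0.2 | 0.8 | 0.6, in favour of music |
| Equal split | same | same | 0 |

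The largest of these is 0.6/5 = 12% of the target difference, and 0.6/2.0 = 0.3 of the standard error at 50 per arm. The sign follows whichever arm loses more of the worse-scoring patients, and the plan gives nothing that settles which arm that would be.

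**4. Propofol.** The plan gives no mean or SD for propofol use, so no shift can be computed. A patient moved to a deeper anaesthetic could have an extreme value, so the effect of excluding or keeping such a patient could be proportionately larger than for the STAI.

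**The case against.** The natural reading of step G is a block that did not work at placement, before any music. The target population is patients operated on under spinal anaesthesia, so a patient without one is arguably outside it. The rule is written in advance and covers both arms. Dropping pre-treatment failures by a criterion unrelated to arm costs precision but not validity. Nor do the documents describe how a failed block is recognised: propofol is titrated to a BIS range (or as respiratory rate allows) and the outcome STAI is taken on day 1. The route from a poor block to exclusion to a 10-point STAI difference is therefore an assumption at each step. The 4 v 1 split also takes the top of an assumed range of 2 to 5 exclusions per 100.

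Most of this stands as a limit on size. A reader might infer that patients certainly will be excluded after music has started, by staff reacting to distress. The documents do not say so. It is a possibility left open by the order of steps and the missing time limit. A reader might also infer that the benefit of music is understated, but the direction cannot be known.

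The objection does not rescue the rule. An early, arm-independent judgement would be nearly harmless, but step G does not confine itself to that case. Applying it in both arms protects the comparison only if failure is called at the same rate and in the same kind of patient in each. With the arm visible and no definition, the plan cannot ensure that.

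**Conclusion.** The point holds in a limited form. Randomised patients are dropped by an undefined rule applied after allocation, with the arm visible and no analysis set to bring them back. The order of events and the rule are in the text; exclusion after music has started is an inference from them.

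The size is unknown and probably modest. Under deliberately unequal assumptions it is about 0.6 STAI points in either direction, and it is zero in expectation if exclusion is unrelated to arm. The power cost is small at any failure share up to the assumed 10%. The change should be made because it removes a source of bias cheaply, not because the plan's figures show that the result would be overturned.

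**What to change.** **Preferred.** Ask every patient for a music genre before surgery. Keep the assignment concealed, for instance in a sealed envelope, and open it in the operating room once the block has been checked, just before headphones would go on. Spinals that fail before that point are then not randomised. Replace step G with wording such as: *Patients whose spinal fails before the assignment is opened are not randomised. Any block failure after that is recorded by arm; the patient stays in the study, completes the day-1 STAI and satisfaction survey, and is analysed in the assigned arm.* Add a sensitivity analysis of propofol use that omits patients converted to another anaesthetic. This changes who is counted and when, not how a failed block is managed. It also means that the first STAI is answered before the arm is known.

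**Minimum, if assignment stays in the preoperative area.** Keep all randomised patients in the primary STAI and satisfaction analyses, and report block failures by arm.

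**Cost.** A short amendment, envelopes in theatre and one extra question for controls. If unrandomised patients are replaced, the enrolment figure of 100 must refer to randomised patients. At an assumed 2% to 5% early failures, consented patients rise to 100/0.98 = 102.04, so 103, or 100/0.95 = 105.3, so 106. That is 3 to 6 more consents and baseline STAIs; at the 2.50 dollars per questionnaire in item 4, 7.50 to 15.00 dollars. Two downsides remain: controls asked for a genre and then given no music may be disappointed, which could touch their ratings, and late conversions may add extreme propofol values to a t-test comparison.

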- 9. Covidien. BISTM Brain Monitoring During TIVA Procedures. Accessed 16 March 2018. http://www.medtronic.com/covidien/en-us/products/brain-monitoring/bis-complete-4-channel-monitor.html

200 has used as 020117 final

10/25/2017

Music therapy versus Control during Total Knee Replacement under Spinal Anesthesia

STATISTICAL CONSIDERATIONS

General Data Analysis Plan: All demographic and clinical variables with continuous measures will be expressed as means and standard deviations; categorical factors will be expressed as proportions. For non-normal data, the medians and inter quartile ranges will be displayed. The distribution of the continuous factors will be examined using the Kolmogorov-Smirnov test. For data that are normally distributed, the one-way ANOVA and Student's t-test will be used to compare groups of data. For data that are not normally distributed, the Kruskal-Wallis and Mann-Whitney tests will be used for comparisons. Chisquare and Fisher's exact tests will be used to analyze categorical data. For all comparisons, a value of p < 0.05 will be considered statistically significant.

Primary Outcome Analysis: Statistical analyses will be performed using SAS for Windows, version 9.2. Student's t-test will be used to compare score from preoperative and postoperative STAI assessment, intraoperative propofol use, and to compare patient satisfaction.

Statistical Power and Sample Size Estimates (if applicable): Sample size (100) was determined using a Cohen's d table assuming a mean STAI anxiety score of 35 (SD = 10) on a scale of 20-80 for control subjects. A difference of STAI score of 5 between two study groups will be clinically relevant. A sample of 50 participants (25 patients per group) will have approximately 85% power to detect a reduction in anxiety score difference of 5 with significance level alpha of 0.05.

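### The SAP gives two unreconciled rules for testing the three primary end points, so the primary test is not uniquely fixed in advance

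*Combined protocol and SAP*

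**What the plan says.** Statistical Considerations holds two instructions in consecutive paragraphs.

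- **General Data Analysis Plan.** "The distribution of the continuous factors will be examined using the Kolmogorov-Smirnov test". Then: "For data that are normally distributed, the one-way ANOVA and Student's t-test will be used to compare groups of data", and "For data that are not normally distributed, the Kruskal-Wallis and Mann-Whitney tests will be used for comparisons". The significance criterion is also set here: "For all comparisons, a value of p < 0.05 will be considered statistically significant".
- **Primary Outcome Analysis.** "Student's t-test will be used to compare score from preoperative and postoperative STAI assessment, intraoperative propofol use, and to compare patient satisfaction". No normality condition and no rank-based fallback is mentioned.

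The outcomes in the second paragraph correspond to the three that protocol item 14.b lists as primary: anxiety, sedation requirements and satisfaction. The sample-size section assumes a "mean STAI anxiety score of 35 (SD = 10) on a scale of 20-80 for control subjects" and adds: "A difference of STAI score of 5 between two study groups will be clinically relevant".

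**The concern.** For a primary end point that fails the normality check, the first paragraph leads to Mann-Whitney and the second to the t-test. No order of precedence is given. Two statisticians could follow the SAP faithfully and report different primary tests, and the choice would be made with the trial data in hand.

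The target changes too. The t-test on means addresses the 5-point difference used for sizing. Mann-Whitney addresses whether scores in one arm tend to be lower than in the other, and gives no estimate of a mean difference. If it became the primary result, the trial would not report directly on the difference it calls clinically relevant.

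**Working it through.** **Inputs from the documents.** STAI control mean 35, SD 10, scale 20–80, difference 5 (sample-size section); 1:1 allocation and 100 participants, so 50 per arm (items 16.a and 16.e); p < 0.05, taken as two-sided because the SAP does not say.

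**Inputs not in the documents.** The shape of the STAI distribution, the distribution of propofol use, and the satisfaction scale. These are assumed below and varied. The SAP also leaves the Kolmogorov-Smirnov step open: no level, no statement of pooled or per-arm testing, and no correction for an estimated mean and SD.

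**1. The plan's own figure.** The SAP gives no rate of disagreement between its rules. Its only related figure is about 85% power with 25 per arm. With non-centrality (5/10)·√(n/2), n = 25 gives 1.77 and an exact two-sided t-test power of 41.0%; n = 50 gives 2.50 and 69.7%. The 85% does not reproduce. That is a separate matter; the 69.7% is the starting point for step 5.

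**2. Can STAI be normal under these inputs?** The floor is (20 − 35)/10 = −1.5 SD for controls and (20 − 30)/10 = −1.0 SD after a 5-point reduction. A true normal would put 6.7% and 15.9% of scores below the scale minimum. Some departure from normality is therefore built in.

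**3. How often do the rules disagree?** 10,000 simulated trials per row, 50 per arm. Fixed rule: t-test always. Selection rule: Mann-Whitney if a Kolmogorov-Smirnov test with Lilliefors critical value rejects at 5% in either arm, otherwise the t-test.

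| Assumed data | Effect | Normality rejected | Fixed rule significant | Selection rule significant | Different conclusion |
|---|---|---|---|---|---|
| STAI normal (35, 10) | none | 9.6% | 5.1% | 5.2% | 0.4% |
| | 5 points | 9.6% | 69.5% | 69.2% | 0.9% |
| STAI normal, rounded, floored at 20 | none | 18.5% | 5.3% | 5.4% | 0.5% |
| | 5 points | 48.9% | 68.5% | 68.5% | 2.8% |
| STAI gamma from 20 (35, 10) | none | 92.8% | 4.7% | 4.8% | 2.7% |
| | 5 points | 94.2% | 85.2% | 79.7% | 8.9% |
| Propofol lognormal, CV 0.5 | none | 88.6% | 4.9% | 5.0% | 3.2% |
| | real effect | 88.3% | 81.4% | 83.8% | 8.0% |
| Satisfaction with ceiling, 0–10 | none | 100% | 5.0% | 4.8% | 4.2% |
| | real effect | 100% | 41.0% | 54.7% | 20.6% |

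The skewed results depend on how the effect is modelled. For gamma STAI and 5 points, disagreement is about 8–9% if the treated SD shrinks with its mean, 14.7% for a constant shift clipped at 20, and 19.9% if the treated SD stays at 10. For lognormal propofol with CV 0.6 and a 20% reduction it is 13.6%. With CV 1.0 and a large effect it falls to 5.9%, because both tests then have power above 90%.

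**4. A different test is not a different conclusion.** In the gamma STAI rows the selection rule switches to Mann-Whitney in about 93% of trials, yet the conclusion changes in 3–9%. Using the uncorrected critical value instead lowers the rejection rate with no effect from about 93% to 16%, so the unspecified detail of the pre-test itself decides which test is used.

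**5. Gain from baseline adjustment.** Adjusting for preoperative STAI with correlation r reduces the SD to 10·√(1 − r²), so the non-centrality at 50 per arm is 2.50/√(1 − r²).

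| r (assumed) | Residual SD | Non-centrality | Power |
|---|---|---|---|
| 0 | 10.0 | 2.50 | 69.7% |
| 0.3 | 9.54 | 2.62 | 74% |
| 0.5 | 8.66 | 2.89 | 82% |
| 0.7 | 7.14 | 3.50 | 93% |

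**The case against.** The strongest reply is that there is no conflict. The general paragraph opens with demographic and clinical variables, while a separately headed paragraph names a test for three specific outcomes; the specific rule governs, and its t-test matches the 5-point target. That is a natural reading, but the text does not state it. The general paragraph also supplies the p < 0.05 criterion for every comparison, so it cannot simply be read as leaving the primary outcomes out. The opposite reading, a t-test subject to the normality check, is also tenable.

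A second reply is that little turns on it. For STAI under the plan's inputs this stands: about 3% disagreement at most. Much of the disagreement in the skewed cases reflects a difference in power between two valid tests, not a false positive.

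A reader might infer more in two ways. One is that the rules would often give opposite answers; the documents contain no skewed distribution that would support this. The other is that the SAP lets the analyst take whichever p-value is smaller. It does not: one rule fixes the test, and the other chooses by a normality test.

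**Conclusion.** The point holds as a gap in pre-specification with limited numerical consequence. Two rules apply to the same three end points and neither is given precedence. For STAI with mean 35, SD 10 and a floor at 20, the conclusion would differ in about 0.4–3% of trials, and both rules keep type I error near 5%. Rates of roughly 8–20% for STAI or propofol, and a similar upper figure for satisfaction, rest on shapes and effects assumed here. The change of target does not depend on these rates: whenever the pre-test rejects normality and the general rule is followed, the primary result no longer estimates the mean difference used for sizing. This is a worthwhile clarification and does not threaten the trial's validity.

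**What to change.** In Primary Outcome Analysis:

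1. State that the Kolmogorov-Smirnov rule does not apply to the three primary end points.
2. Fix the between-group difference in means with its 95% CI as the primary analysis of each.
3. For anxiety, analyse postoperative STAI adjusted for preoperative STAI. Items 17.B and 17.E already collect both, so no new data are needed.
4. Report Mann-Whitney as a sensitivity analysis only.

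The cost is a few sentences, settled before the data are examined. The downside is small: if scores are strongly skewed, a mean-based test may have a little less power than a rank test. This is not certain, since in the gamma STAI case with a shrinking treated SD the t-test was the more powerful (85% against 79% for Mann-Whitney).

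### The primary STAI analysis does not define its outcome and leaves the preoperative score unused; the order of first STAI and randomisation should be fixed along with it

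*Combined protocol and SAP*

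**What the plan says.** In Statistical Considerations, Primary Outcome Analysis, one sentence covers all three primary end points: Student's t-test "will be used to compare score from preoperative and postoperative STAI assessment, intraoperative propofol use, and to compare patient satisfaction". Nothing there names an outcome form, a contrast or a covariate for the STAI.

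Two other places help with the contrast. The General Data Analysis Plan says that for normal data the "t-test will be used to compare groups of data". The sample size paragraph says "A difference of STAI score of 5 between two study groups will be clinically relevant". Item 14.b lists anxiety levels as a primary end point without a time point or form.

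On the order of steps:

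- Item 16.e: "Upon enrollment in the study, participants will be randomized 1:1 to either the investigational group".
- Item 17.A repeats the randomisation. Item 17.B follows with "After enrollment, all patients will complete a State-Trait Anxiety Assessment (STAI) questionnaire", and then says that the Music Therapy "group will be asked to choose a genre of music that they would like to listen to during the operation".
- The table in item 17.e has a row for randomisation on the day of surgery. The next row reads "Choosing music genre, completing STAI Questionnaire".
- Item 17.E has all patients complete the STAI again on postoperative day 1.

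**The concern.** Read literally, the sentence describes a pre-versus-post test, which does not estimate the effect of music. Read as a between-arm test, it still leaves two candidate outcomes, the day-1 score and the change. They have different power and can give different answers on the same data. If the choice is made after the data are seen, the 5% error rate no longer holds.

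The preoperative STAI is collected from everyone, yet an unadjusted day-1 test makes no use of it. To the extent that the first score predicts the second, precision is given up.

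The order of steps matters for the same reason. A score completed after a patient knows the arm may already reflect the allocation. That cannot affect an unadjusted day-1 comparison. It can bias any analysis that subtracts the baseline or adjusts for it.

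**Working it through.** **Inputs from the documents.** Difference 5, SD 10 and alpha 0.05 (sample size paragraph); enrolment of 100 (item 16.a) randomised 1:1 (item 16.e), so 50 per arm.

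**Assumptions.** Two-sided test, since sidedness is not stated. SD 10 is the SD of a single score, equal at both times. The pre-post correlation r is not given, so a range of 0.3 to 0.7 is shown.

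**The plan's own figure.** The sample size paragraph claims about 85% power with 25 per group. A two-sample t-test with these inputs gives 41% at 25 per arm and 70% at 50 per arm (two-sided), so the figure is not reproduced. That, and the conflict between 100 and 50 participants, are separate problems. The comparison below uses 50 per arm.

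**Method.** Power comes from the noncentral t distribution with noncentrality 5 / (SD × √(2/50)) = 5 / (SD × 0.2). The SD depends on the outcome form:

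- Day-1 score: SD = 10, df 98. Noncentrality 5/2 = 2.5; power 69.7%.
- Change score: SD = 10 × √(2(1 − r)), df 98. At r = 0.5 this is 10, the same as day-1. Below 0.5 it is larger, above 0.5 smaller.
- ANCOVA: residual SD = 10 × √(1 − r²), df 97. At r = 0.5 this is 8.66; noncentrality 5/1.732 = 2.89; power 81.5%.

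| r (assumed) | Day-1 t-test | Change-score t-test | ANCOVA | ANCOVA 95% CI half-width |
|---|---|---|---|---|
| 0.3 | 69.7% | 55.3% | 73.7% | 3.79 |
| 0.4 | 69.7% | 61.8% | 77.1% | 3.64 |
| 0.5 | 69.7% | 69.7% | 81.5% | 3.44 |
| 0.6 | 69.7% | 79.0% | 87.2% | 3.18 |
| 0.7 | 69.7% | 89.2% | 93.4% | 2.83 |

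The half-width is t × SD × 0.2. For the day-1 t-test it is 1.984 × 10 × 0.2 = 3.97 points. Simulated ANCOVA power (20,000 trials per r) was 72.8%, 76.8%, 81.8%, 86.8% and 93.2%, in agreement with the table.

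**Cost of leaving the form open.** Under no effect (200,000 simulated trials per r), each t-test alone rejects in 5.0% of trials. At least one of the two rejects in 8.7%, 8.9%, 9.1%, 9.2% and 9.4% for r = 0.3 to 0.7.

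**Step order.** Randomisation is tied to the moment of enrolment and the first STAI comes after enrolment. Item 17 lists randomisation (A) before the STAI (B), and the table puts the STAI in the row after randomisation. This suggests, without stating it, that the first STAI follows randomisation. Genre choice is offered only to the Music Therapy arm, so it reveals the arm. Item 17.B puts the STAI before that choice; the table row names the choice first. Nothing requires the first STAI to be finished before the arm is known.

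**Sensitivity to that order.** Suppose knowing the arm shifted the music-arm preoperative score by 1 point (an assumption; the documents show no shift). The resulting bias is 0 for the day-1 t-test, r points (0.3 to 0.7) for ANCOVA and 1 point for the change score.

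**The case against.** The strongest reply is that little is actually undefined. The general plan compares groups, the power statement concerns two study groups, and propofol use and satisfaction in the same sentence have no preoperative value. A pre-versus-post test is therefore unlikely to be meant. This stands for the contrast, but it does not settle day-1 score against change.

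Second, an unadjusted day-1 t-test is valid, so ANCOVA is a gain in efficiency and not the correction of an error. That also stands. The gain depends on r: at r = 0.1 and 0.2, ANCOVA power is 70.1% and 71.4%, barely above 69.7%. With one score before surgery and one the day after, a low r cannot be excluded. Even so, the adjustment costs one degree of freedom, and ANCOVA power exceeds that of both t-tests at every r in the table.

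Third, the order of steps affects only analyses that use the baseline, item 17.B already puts the STAI before the revealing step, and a table of durations is weak evidence of sequence. This is fair. It is a reason to settle the order together with the covariate, not to leave it open.

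Fourth, the power claim is attached to 25 per group. At 25 per arm the figures are 41% for the day-1 t-test (half-width 5.69), 31% to 61% for change and 44% to 68% for ANCOVA, for r from 0.3 to 0.7. All are lower, but the direction is the same.

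**Conclusion.** The concern holds. The primary STAI result is not uniquely defined, the preoperative score is not used as a covariate, and the first STAI is not placed before randomisation. A valid analysis can be inferred, so this is a matter of specification and precision and does not make the trial invalid.

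At 50 per arm, ANCOVA would raise power over the day-1 t-test by about 4 percentage points at r = 0.3 and about 24 at r = 0.7. Freedom to pick between the two t-tests would nearly double the type I error. These sizes rest on the assumed r, on SD 10 applying to a single score and on a two-sided test. The documents do not show that any baseline shift occurs; the order matters because they do not rule one out.

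**What to change.** Replace the STAI part of the Primary Outcome Analysis sentence with:

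> The primary STAI analysis is the between-group difference (Music Therapy minus No Music) in postoperative day 1 STAI score from an ANCOVA with treatment group and preoperative STAI score as terms, reported with its 95% CI; no within-group test is used for inference.

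State the order in items 16.e and 17.A–B and in the item 17.e table as consent, STAI, randomisation, genre choice, so that the baseline is complete before the arm is known.

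The same edit should say which STAI score (state or trait) is meant and how the ANCOVA sits with the general rule that non-normal data go to a Mann-Whitney test, since neither is settled at present.

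The cost is SAP wording and a stated order for steps within the same preoperative visit. No data, patients or visits are added.
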